9.0 Data and Specimen Long Term Storage and Use

9.1 *If you will store data or specimens for future use, describe where you will store the data or specimens, how long they will be stored, and how and by whom the data or specimens will be accessed:*

Subjects will be assigned a coded description, the key to which will be stored in a locked safe, in a locked room, separate from other study materials. All paper records from the

study, with the exception of the consent form and the MRI screening form, will be identifiable only by this subject number, and all forms will be kept in a locked file cabinet. Electronic data will be accessed via password protected computer and password protected server.

9.2 For specimens, list the data to be stored or associated with each specimen:

All paper records containing participant identity will be stored in locked cabinets and available only to authorized research staff.

9.3 Describe the procedures to release data or specimens outside of the research team, including the process to request a release, approvals required for release, who can obtain data or specimens, and what data will be provided with specimens:

In an effort to foster open neuroscience and reproducible results, anonymized data collected as a part of this study may be made openly available on the internet, in one of the various repositories for housing such data. All data will be de-identified using standards conforming to HIPAA guidelines. For example all high-resolution images will be defaced to avoid the possibility of the subject being identified from the scans. Only subject ages will be released, not subject birthdates, we will not include any subjects whom are old enough to be uniquely identified by age alone. New subject identifiers will be assigned, such that data will not be mappable back to internal subject identifiers. Subjects with rare, and potentially identifying brain abnormalities will not be included in the release.

There are several ways in which openly sharing this data will be beneficial to society. It makes it possible for other researchers to validate any scientific results that we may find. It is a valuable educational resource for new researchers to learn how to analyze these types of data. Also, by allowing other researchers to use (or reuse) the data, we are reducing the amount of time and money required to perform similar scientific research.

9.4 Describe the identifiers to be included with stored data or specimens, as well as any key or code that could be used to make them identifiable. Describe where the code will be stored, who will have access to it, and when it will be destroyed:

Subjects will be assigned a coded description, the key to which will be stored in a locked safe, in a locked room, separate from other study

materials. Codes will not be based on any participant-relevant information. All identifiable data, including the code linking participant name to their study ID, will be destroyed after 7 years.

9.5 *Please select the identifiers you will obtain (whether directly from participants or from another source), including but not limited to:*

	Name
	Geographical subdivisions smaller than a state, including street address, city, county, precinct, zip code, and equivalent geocodes (note, the initial three digits of a zip code are not considered identifiable)
	Elements of dates (except year) for dates directly related to an individual, including birth date, admission date, discharge date, date of death, and single year of age over 89 and all elements of dates (including year) indicative of such age (note, such ages and elements may be aggregated into a single category of age 90+)
	Phone numbers
	Fax numbers
	Electronic mail addresses (e-mail)
	Social Security numbers
	Medical record numbers
	Health plan beneficiary numbers
	Account numbers
	Certificate/license numbers
	Vehicle identifiers and serial numbers, including license plate numbers
	Device identifiers and serial numbers
	Web Universal Resource Locators (URLs)
	Internet protocol (IP) address numbers
	Biometric identifiers, including finger and voice prints (audio recording)
	Full face photographic images and any comparable images (including video recording)
	Student record number or identification number
	User name for online or computer accounts
	Any other unique identifying number, characteristic, or code (note this does not mean the unique code assigned by the investigator to code the data): Click here to explain.

10.0 Sharing of Results with Subjects

10.1 *Describe whether you will share results (study results or individual subject results, such as results of investigational diagnostic tests, genetic tests, or incidental findings) with subjects or others (e.g., the subject's primary care*

physician). If so, describe how you will share the results and include this information as part of the consent document. Upload materials you will use to explain the results to subjects:

We will not share any results with the study participants.

Specific to incidental neuroimaging findings: The Human Neuroimaging Lab at Virginia Tech has a standardized approach to incidental findings across approximately 60 currently active protocols (including scanning over 150 individuals with AUD).

Moreover, our process is consistent with the best practices recommendations of the NIMH “MRI Research Safety and Ethics: Points to Consider” whitepaper (https://www.nimh.nih.gov/about/advisory-boards-and-groups/namhc/reports/mri-research-safety-ethics_33826.pdf). Furthermore, our procedures conform with those reported in the literature as appropriate for our research setting. During the consenting process, participants are informed that the scans that will be performed in the study are not the same as those that would be used in a clinical setting, and thus have limited diagnostic value. Further, some of the scans require subsequent data analysis and would never be read by a neuroradiologist. As is common and acceptable in many academic institutions, we do not have a neuroradiologist on staff to read every scan. Our policy (which is communicated to all participants verbally and written in the consent document): “This is not a study for diagnostic purposes and your brain images will not be read by a radiologist. If, by chance, something abnormal is observed, you will be informed of this and counseled as to what clinical referral would be appropriate as we are not qualified to make any diagnosis, nor is this fMRI of diagnostic quality for medical purposes.” We also communicate, however, that we will err on the side of caution in communicating with them if we do observe a possible abnormality.

11.0 Study Timelines

11.1 Describe:

- *The duration of an individual subject’s participation in the study (for example, 1 hour, 2-4 weeks, 3-5 years).*
- *The amount of time expected to enroll all study subjects (weeks, months, years, etc.)*
- *The amount of time expected for the investigators to complete this study including primary data analyses.*

Participants will participate in one rtfMRI session. The participants will lie still in the MR scanner for a total of no more than 90 minutes, and MRI sessions will not exceed two hours. The brief cue generation interview, completed prior to the scanning appointment, is expected to take 20 minutes, and will not exceed one hour. We will retain personally identifiable study data for a period of seven years after completion of the study. After the period of 7 years has passed, we will destroy any personally identifiable study data. Recruitment and enrollment

is anticipated to last 18 months. From start to completion, including data analyses, this study is anticipated to last two years.

12.0 Inclusion and Exclusion Criteria

12.1 Describe how you will screen individuals for eligibility. When will screening occur and what procedures will you use? Upload any screening scripts or surveys to Protocol Management:

Potential subjects will be initially screened over the phone or in person. Individuals meeting inclusion/exclusion criteria for the study, as determined by the pre-consent screening form will be enrolled.

12.2 Describe the eligibility criteria that define who will be included and who will be excluded from enrollment for each procedure of your study. Include any geographic criteria (e.g., Virginia Tech undergraduate students, a national sample of adults with engineering degrees, minors aged 8-12 in the New River Valley, university faculty in Virginia and Paris, France):

Inclusion criteria for signing consent will require that participants: (1) drink alcohol (2) be 21 years of age or older,

Exclusion criteria include: (1) meeting moderate to severe DSM-5 criteria for substance-use disorders other than alcohol, nicotine, or marijuana, (2) having a current diagnosis of any psychotic disorder, (3) having a history of seizure disorders or a traumatic brain injury they have not fully recovered from, (4) reporting current pregnancy or lactation.

12.3 Indicate specifically whether you will include or exclude each of the following special populations: (You may not include members of these populations as subjects in your research unless you indicate them in the description of your subject population.)

- *Minors, as defined by state law where the study is performed (infants, children, teenagers)*
- *Pregnant women (can be included in minimal risk studies by mentioning in section 13.1)*
- *Prisoners (including all incarcerated individuals)*
- *Adults not capable to consent on their own behalf*

This project will focus on individuals with alcohol use disorder, aged 21 or over. We will not include individuals under the age of 21 in compliance with Virginia state law. Vulnerable subjects, such as individuals with cognitive impairments, minors, prisoners, and pregnant women will be excluded.

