1.0 Study Summary

Study Title	Brain Network Modulation and Alcohol Use
Study Design	This study seeks to investigate brain network modulation in individuals with alcohol use disorder (AUD). Enrolled participants will undergo a real-time fMRI scan and may be asked to complete corresponding questionnaires which will be submitted to the IRB for approval prior to use.
Primary Objective	Directly test the ability to modulate neural activity as a function of AUD severity using real-time fMRI.
Secondary Objective(s)	N/A
Study Population	Individuals who drink alcohol
Sample Size	50 participants
Research Intervention(s)/ Investigational Agent(s)	Data collection will include MRI data, including a real-time modulation task in-scanner, and relevant questionnaires.
Study Duration for Individual Participants	Participants will participate in one rtfMRI session. Prior to their fMRI, they will complete a brief interview to generate cues for use during their scan. We will retain personally identifiable study data for a period of seven years after completion of the study. After the period of 7 years has passed, we will destroy any personally identifiable study data.
Acronyms and Definitions	AUD=Alcohol Use Disorder AUDIT= Alcohol Use Disorders Identification Test fMRI=Functional Magnetic Resonance Imaging rtfMRI=real-time fMRI DMN=Default Mode Network FBRI=Fralin Biomedical Research Institute VTC=Virginia Tech Carilion HNL=Human Neuroimaging Laboratory BAAD = Brief Assessment of Alcohol Demand DD = Delay Discounting

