2.0 Objectives

2.1 Describe the purpose, specific aims, or objectives of this study:

This study directly tests the ability to modulate neural activity as a function of AUD severity using real-time fMRI.

2.2 State the hypotheses to be tested:

We hypothesize that individuals with lower AUD severity will have a significantly higher correlation (indicating better modulation ability) than individuals with higher AUD severity.

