5.0 Study Design and Statistical Analysis Plan

5.1 *Describe the basic study design/approach (e.g., qualitative study using five focus groups of first year students to describe assimilation into the university community; randomized controlled trial of a behavioral change intervention to increase dietary intake of whole grains; pre- post-test evaluation of new pedagogical techniques to improve adult literacy):*

50 participants who drink alcohol, including those with AUD, will be recruited and consented into a real-time study intended to assess the relationship between AUDIT score and neural modulation. There are two neuromodulation tasks, which they may complete one or both of. The "DMN" neuromodulation task has them attempt to "focus/wander". The "BAAD" neuromodulation task instructs participants to modulate their brain activity toward a craving for alcohol or orient it toward a future goal. If there is time, and the participant is interested, they will also be given the opportunity to complete the other task to which they weren't initially assigned.

5.2 *Describe corresponding data analysis plan/approach (e.g., content analysis of focus group transcripts; descriptive analysis followed by linear regression modeling; nonparametric analysis of pre- and post-test measures):*

GLM-based analysis will be performed using AFNI (Cox, 1996). We will perform slice timing correction, motion correction, and spatial smoothing (Gaussian kernel with full-width-at-half-maximum of $2.0 \times$ the voxel size). The stimulus paradigms will be convolved with an ideal hemodynamic response function, and linear regression analysis will be performed to obtain linear regression coefficients (beta-weights) and t-statistic maps. In addition, we will perform support vector machine analysis using the 3dsvm AFNI plugin software we have developed.

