participant will be asked to describe the most positive event that could realistically happen at several time points (e.g. 1 week out, 5 years out, etc). For each time point, the participant will be asked to integrate the event and sensory information into concise descriptions to be used in generating images. Participants may also choose to provide images of loved ones involved in these events. Providing images of loved ones is completely optional. Any images of loved ones provided will be kept on secure, password protected servers. The eye-tracking scan has the participant watch a moving dot on the screen for a brief period of time. If the staff has reason to be concerned about the quality of a localizer or anatomical scan (for example due to motion in the scanner), the scan will be repeated. If a participant decides to discontinue their participation, some parts of the scan will not be completed.

Breath Alcohol Concentration (BrAC) will be recorded upon arrival, with a required BrAC less than 0.003 g/dL to begin study procedures. Once their BrAC is cleared, participants will complete an Alcohol Withdrawal Symptoms questionnaire to assess alcohol withdrawal and an out-of-scanner Delay Discounting task (DD). Lastly, prior to scanning participants will complete a series of questionnaires (e.g. Socioeconomic Status (SES), Alcohol Use Disorder Identification Test (AUDIT), Alcohol Reinforcement Questionnaire).

Following the MRI scan, participants will be asked to rate the images from the MRI tasks. They will provide their feedback using a slider (ex: scale of 1-9) on qualities such as valence, arousal, and craving.

Participants will also be asked to complete a relevant post-scan questionnaire asking about their subjective experience during the MRI scan, which would include valuable data such as their effort level, if they were able to stay awake, and their confidence in the task (see attachment). Any questionnaires used will receive approval from the IRB prior to use with participants. Questionnaires used will supplement these findings with relevant information. Prior to study activities, participants will provide consent and review their MRI screening form with the researcher.

8.2 *Provide a description of:*

- *All research procedures being performed*

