- *If the study has more than one procedure, session, and/or subject population, describe each procedure, session, and/or study population separately. For complex studies, you are encouraged to include a figure or chart.*

Participants will be recruited from the community via posted flyers, word of mouth, and electronic advertisements (e.g., Craigslist, Facebook). Participants will be contacted if they have given prior permission (through previous informed consent form) or by completion of a confidential pre-screening questionnaire. Upon contact, participants will

complete an MRI screening form to assess eligibility. At this time participants may be scheduled for their session if they are eligible. Cue questions used for image generation may be asked during this phone call, or at a later time prior to their MRI appointment. During cue generation the participant will be asked to describe the most positive event that could realistically happen at several time points (e.g. 1 week out, 5 years out, etc). For each time point, the participant will be asked to integrate the event and sensory information into concise descriptions to be used in generating images. Participants will also be informed at this time that they may provide images of loved ones if they would like, although this will be in no way a requirement. Any images of loved ones provided will be kept on secure, password protected servers.

Breath Alcohol Concentration (BrAC) will be recorded prior to beginning to study procedures. Participants will be asked to come back another day if they come to their session appointment with a BrAC > 0.003 g/dL. Participants are required to refrain from drinking before beginning assessments in the lab. They will also complete an Alcohol Withdrawal Symptom questionnaire and an initial Delay Discounting (DD) task. DD (a measure of the temporal window) examines the devaluation of monetary rewards as a function of delay to their receipt. These computerized assessments present hypothetical choices between smaller, sooner and larger, later rewards available at a range of delays. Lastly, prior to scanning participants will complete a series of questionnaires (e.g. Socioeconomic Status (SES), Alcohol Use Disorder Identification Test (AUDIT), Alcohol Reinforcement Questionnaire).

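### Do the mixed descriptions of who is enrolled, and the absence of any AUDIT target, call for a change to recruitment?

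*Combined protocol and SAP*

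**What the plan says.** The population is described in two ways.

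- **Drinkers, with or without AUD.** Section 12.2: "Inclusion criteria for signing consent will require that participants: (1) drink alcohol (2) be 21 years of age or older". Section 5.1: "50 participants who drink alcohol, including those with AUD, will be recruited". Section 3.3 and the Study Population row of the summary in 1.0 say the same in substance.
- **People with AUD.** Section 12.3: "This project will focus on individuals with alcohol use disorder, aged 21 or over". The Study Design row of the summary: "This study seeks to investigate brain network modulation in individuals with alcohol use disorder (AUD").

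The hypothesis in 2.2 is that "individuals with lower AUD severity will have a significantly higher correlation (indicating better modulation ability) than individuals with higher AUD severity". Sections 3.3 and 5.1 make AUDIT score the measure of severity. AUDIT is listed among the visit-day forms in 8.1 and 8.2: "prior to scanning participants will complete a series of questionnaires".

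Screening comes earlier. Section 12.1 states "Potential subjects will be initially screened over the phone or in person", and 8.2 says people may be contacted after making themselves known "by completion of a confidential pre-screening questionnaire". The screening forms and the recruitment flyer are attachments and are not shown. Section 14.1 plans on r = 0.4, alpha 0.01 and power 0.8, derives 42, and sets the sample at 50. It does not say to which population or AUDIT range r = 0.4 refers.

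**The concern.** The hypothesis needs people at both ends of the severity scale. Taken literally, 12.3 suggests a sample with AUD only, which could cut off the low end. Taken literally, 12.2 allows a sample made up mostly of light drinkers, which could leave the high end thin. In the visible text AUDIT is first recorded on the day of the scan, too late to shape enrolment, and no target range, quota or running check is described.

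For a fixed slope, less variation in AUDIT means a smaller correlation and less power. A null result could then reflect a narrow sample rather than the absence of a relationship, after all 50 scans had been spent. A reader might also doubt which population the correlation describes.

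**Working it through.** **Step 1: which statement governs.** Section 12.2 is the eligibility criterion. Sections 5.1, 3.3 and the summary's population row agree with it. The sentence in 12.3 answers a template question about minors, pregnant women, prisoners and adults unable to consent; it describes an emphasis and excludes nobody. The summary's design row names the research topic. Staff who follow the protocol therefore enrol drinkers aged 21 or over at any severity, and neither end of the scale needed by 2.2 is shut out.

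**Step 2: the plan's own figure.** For one correlation tested against zero, the Fisher approximation gives N = ((z_alpha + z_power) / atanh(r))² + 3, with atanh(0.4) = 0.4236.

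- Two-sided 0.01: ((2.576 + 0.842) / 0.4236)² + 3 = 68.1, so 69.
- One-sided 0.01: ((2.326 + 0.842) / 0.4236)² + 3 = 58.9, so 59.

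Neither gives the 42 in 14.1. At n = 50 exact power is 63.4% two-sided and 72.6% one-sided. That shortfall is a separate sample-size matter. It is present before AUDIT spread is considered and should carry no weight here.

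**Step 3: what spread could do.** Inputs: r = 0.40, n = 50 and alpha = 0.01 from 14.1. Sidedness is not stated, so both are shown. Let u be the enrolled AUDIT SD divided by the SD at which r = 0.40 holds. The documents give neither SD, so u is an assumption. With slope and residual SD held fixed,

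r′ = 0.4u / √(0.84 + 0.16u²).

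For example, u = 0.8 gives 0.32 / √0.9424 = 0.330. Power is from the exact distribution of the sample correlation under bivariate normality (critical |r| 0.361 two-sided, 0.328 one-sided).

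| u | r′ | Power, two-sided | Power, one-sided |
|---|---|---|---|
| 0.5 | 0.213 | 13.7% | 20.1% |
| 0.7 | 0.292 | 30.5% | 40.0% |
| 0.8 | 0.330 | 41.2% | 51.4% |
| 1.0 | 0.400 | 63.4% | 72.6% |
| 1.2 | 0.464 | 81.3% | 87.4% |
| 1.25 | 0.479 | 84.7% | 90.0% |

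From u = 1, two-sided power moves by 41.2 − 63.4 = −22.2 points at u = 0.8 and by 84.7 − 63.4 = +21.3 points at u = 1.25. Nothing in the documents says on which side of 1 this trial falls.

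**Step 4: validity.** If modulation is unrelated to AUDIT, the test keeps its error rate whatever the AUDIT spread. If the relationship is linear, the regression slope is estimated without bias at any spread; only its precision changes. AUDIT is scored for the people in the analysis, so the achieved distribution will be known. Showing it, with the slope and its interval, beside the correlation is ordinary reporting, and would let a reader see whether a null came from a narrow sample.

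**Step 5: what banded enrolment would cost.** AUDIT would have to be taken at screening, which rests on verbal consent; written consent comes only at the MRI session (24.1, 25.2). The key predictor would then precede the scan by an unstated interval unless it were repeated. Section 14.3 gives no screening yield, and 11.1 allows 18 months for 50 people, about 50 / 18 = 2.8 a month, so holding places for a rare band could mean turning eligible volunteers away. The correlation would also depend on the bands chosen.

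**The case for a change.** The strongest case for acting is that severity is the only question this study asks, and the documents neither plan nor check the variable that carries it. The leaning towards AUD is not confined to two sentences: 3.2 asks about AUD individuals, and 18.1 speaks of alcohol dependence. Moving an existing questionnaire to an existing screening contact seems cheap, and since recruitment is by advertising and a contact database, no representative sample would be lost. Reporting the AUDIT distribution afterwards explains a weak result but does not restore the power.

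Much of this is correct. Power does depend on spread, no visible section sets a range, and disclosure afterwards recovers nothing. What does not follow is that the current design is wrong or worse. Sections 3.2 and 18.1 give background and benefits; they are not entry rules. Open enrolment of drinkers may give a narrow or a wide AUDIT spread, and the documents do not let one say which. The unseen screening forms and flyer may already address severity, although that cannot be relied on in either direction. A stated AUDIT range and a source population for r = 0.40 would be welcome detail, but their absence does not alter whom the trial enrols or how its main relationship is tested.

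**Conclusion.** No change is needed. The population conflict is a slip of wording: the operative criterion and three other statements agree on drinkers aged 21 or over, with or without AUD, and aligning 12.3 and the design row would alter nothing the trial does. The silence on AUDIT spread is a gap that analysts can fill by reporting the observed AUDIT distribution and the slope with the correlation. Whether to sample openly or by severity band is a fair trade-off on which statisticians would differ.

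The possible effect is large in either direction (two-sided power from 14% to 85% for u from 0.5 to 1.25), but it is an illustration with no anchor in the documents and does not show that this trial loses. The conclusion assumes that 12.2 is applied as written. A screening form that in practice admitted only people with AUD would make the conflict one of substance; nothing visible suggests that.
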